Appendix 4: Outreach One Pager

HEADING

ImmunoCARE: Rapid, Accurate COVID Testing to Reduce Hospitalization of Immunocompromised Individuals

INTRO

Are you at high risk of hospitalization from COVID-19 infection due to age or a compromised immune system? The ImmunoCare study aims to reduce that risk. Scripps Research – a renowned biomedical research institute – and Cue Health, a leading health care technology company that develops portable diagnostic tests for at-home use, are launching the ImmunoCARE Study.

SUBHEADING

More on The ImmunoCARE Study

ImmunoCARE is an innovative research project to study whether repeated at-home tests, on-demand telemedicine, and quick delivery of medication for those who test positive for COVID-19 can reduce COVID-19 severity in immunocompromised people and those over 65.

ImmunoCARE will enroll 10,000 participants. Half of participants will test for COVID-19 and seek care as they normally would; the other half will receive 10 at-home COVID-19 tests per month from Cue Health for themselves and others in their household. All participants will be asked to complete monthly surveys about COVID-19 exposure, infection, and hospitalization.

Who can enroll

ImmunoCARE is available to individuals who are moderately to severely immunocompromised or are 65 and older. Participants will provide documentation from health claims data confirming their diagnosis and age. Additional criteria for enrollment can be found at immunocare.scripps.edu or scan the QR code, the link below.

Our thanks to you

As our thanks for your participation, all eligible participants will receive a series of Amazon gift cards as compensation throughout the study.

Questions?

If you have any questions about the study, feel free to reach out to the study team at [contact].[contact] or leave a message at [contact].

Appendix 5: Invitation Email

SUBJECT LINE:

Immunocompromised and concerned about COVID-19?

PREHEADER:

Join The ImmunoCARE study which aims to reduce hospitalizations

BODY:

Dear [FIRST NAME],

Are you at high risk of hospitalization from COVID-19 infection due to a compromised immune system or age? The ImmunoCare study aims to reduce that risk. Scripps Research – a renowned biomedical research institute – and Cue Health, a leading health care technology company that develops portable diagnostic tests for at-home use, are launching the ImmunoCARE Study.

ImmunoCARE is an innovative research project designed to examine whether a combination of repeated at-home tests, on-demand telemedicine, and quick delivery of Paxlovid after testing positive for COVID-19 can reduce severe outcomes and hospitalization of people just like you.

We can only succeed in this research with your help. Eligible participants will take part in a 4- to 8-month study and may receive at-home diagnostic tests free of charge.

Learn more and take our eligibility survey today.

CTA

LEARN MORE

Take Care,

The ImmunoCARE Study Team

Appendix 6: You're Eligible Email

SUBJECT LINE:
Welcome to the ImmunoCARE
PREHEADER:
Download the study app today!
BODY COPY:
Dear [FIRST NAME],
Thank you for your interest in participating in the ImmunoCARE Study. We are pleased to inform you that you've met all of the eligibility criteria!
The first step is to download the study app, MyDataHelps. Once you do, you will create a new account and provide your consent to participate. After that, you will be on your way to helping researchers learn more about how to keep people safe from severe COVID-19 infection.
Get started today!
CTA:
DOWNLOAD APP
Take Care,
The ImmunoCARE Study Team
Questions? Reach out to us at [contact]

Appendix 7: You're Not Eligible Email

SUBJECT LINE:

Thank you for your interest in ImmunoCARE

PREHEADER:

We appreciate your willingness to join our study

BODY COPY:

Dear [FIRST NAME],

Thank you for your interest in participating in the ImmunoCARE Study. Unfortunately, you did not meet the study's eligibility requirements at this time.

We greatly appreciate your time and commitment to advancing research to improve COVID-19 outcomes.

Take Care,

The ImmunoCARE Study Team

Appendix 8: Consent Reminder Email

SUBJECT LINE:

Your ImmunoCARE registration is incomplete

PREHEADER:

Please complete your ImmunoCARE consent

BODY COPY:

Dear [FIRST NAME],

Thank you for your interest in the ImmunoCARE Study. We appreciate your willingness to help advance research on reducing COVID-19 hospitalizations for immunocompromised individuals. You are still eligible to participate!

Your consent is required to proceed with participation in this research study. To access the ImmunoCARE consent, open your MyDataHelps app.

If you have any questions about the consent process, you may contact us at [contact].

Thank you again for your participation in this critical research study to reduce COVID-19 hospitalizations.

Take Care,

The ImmunoCARE Study Team

If you have any questions, please reach out to the study team at [contact]

Appendix 9: Baseline Survey Reminder Email

SUBJECT LINE:

Reminder: Your ImmunoCARE survey is waiting!

Alternate subject line: Don't forget to complete your first survey

PREHEADER:

Take the survey today!

BODY COPY:

Dear [FIRST NAME],

Thank you for joining the ImmunoCARE Study. The next step is to complete the Baseline Survey, which asks questions about your demographic information and health conditions. This survey will help researchers understand where you are starting the study from and how the study progresses.

This survey should only take a few minutes. Once you complete this survey, you will earn a \$20 Amazon gift card to thank you for your time.

Thank you again for your participation.

Take Care,

The ImmunoCARE Study Team

Appendix 10: Monthly Survey Reminder Email 1

It's time for your monthly ImmunoCARE survey
PREHEADER:
Take the survey today!
BODY COPY:
Dear [FIRST NAME],

As a valued participant in the ImmunoCARE Study, your survey responses are of critical importance to researchers.

It's time to take this month's survey to share whether you have had any COVID-19 exposures or infections since we last heard from you.

The survey should only take a few minutes of your time, and you will receive an Amazon gift card for answering.

Thank you again for your time and participation in ImmunoCARE.

Take Care.

SUBJECT LINE:

The ImmunoCARE Study Team

Appendix 11: Monthly Survey Reminder Email 2

SUBJECT LINE:

Do you have a minute for ImmunoCARE?

PREHEADER:

Your monthly survey only takes a few minutes

BODY COPY:

Dear [FIRST NAME],

Do you have a minute? A minute or two is all it takes to complete this month's ImmunoCARE survey.

By letting us know if you've been exposed to, infected with, or hospitalized from COVID-19 in the past month, you're helping advance research on reducing hospitalizations and improving outcomes for immunocompromised individuals.

Once you complete your survey, you will receive a code for your Amazon gift card as our thanks to you.

Thank you again for your time and participation in ImmunoCARE.

Take Care,

The ImmunoCARE Study Team

Appendix 12: Your Gift Card is Ready To Claim Email

SUBJECT LINE:

Our gift to you for participating in ImmunoCARE

PREHEADER:

Your Amazon gift card code is ready

BODY COPY:

Dear [FIRST NAME],

We are grateful for your participation in the ImmunoCARE Study. To thank you, we are pleased to give you an Amazon gift card for completing a series of steps throughout the study.

Your gift card for [INSERT AMOUNT] is ready to use. Login to your My Data Helps account to access your Amazon gift card code.

Thank you again for your valued participation in ImmunoCARE.

Take Care,

The ImmunoCARE Study Team

Appendix 13: ImmunoCARE Landing Page

The ImmunoCARE Study:

Rapid, Accurate COVID Testing to Reduce Hospitalization of Immunocompromised Individuals

About the study

The risks associated with COVID-19 infection is higher for immunocompromised individuals and people over 65 than the general public. ImmunoCARE is an innovative research project to study whether repeated at-home tests, on-demand telemedicine, and quick delivery of medication for those who test positive for COVID-19 can reduce COVID-19 severity in immunocompromised people.

ImmunoCARE is a joint research project from Scripps Research – a renowned biomedical research organization – and Cue Health, a leading health care technology company that develops portable diagnostic tests for at-home use.

Who can enroll

ImmunoCARE is available to individuals who are moderately to severely immunocompromised. Participants will provide documentation from a medical provider confirming their diagnosis.

Additional inclusion criteria includes:

- Living in the United States
- 18 years or older
- Vaccinated against COVID-19
- Willing and able to participate in study interventions including:
 - Use of a compatible smartphone, including camera and bluetooth
 - Willing and able to share health insurance claims data from Medicaid, Medicare, or an Anthem plan if over 65 and not otherwise immunocompromised
 - Completing Surveys
 - Use of Cue Health App and tests
 - Use of MyDataHelps by Web or App
- Immunocompromised, including
 - Symptomatic HIV
 - Graft versus host disease
 - Immunoglobulin deficiency/Immunodeficiency
 - Immunosuppressive therapy
 - o Leukemia
 - Lymphoma (Hodgkin or non-Hodgkin)
 - Metastatic Cancer
 - Multiple Myeloma
 - Solid organ malignancy
 - Transplant, hematopoietic stem cell
 - Transplant, solid organ
 - 65 years or older

What we will ask you to do

ImmunoCARE will enroll 10,000 participants. Half of participants will test for COVID-19 and seek care as they normally would; the other half will receive at-home COVID-19 tests from Cue Health for themselves and others in their household. All participants will be asked to complete monthly surveys about COVID-19 exposure, infection, and hospitalization.

Our thanks to you

As our thanks for your participation, all eligible participants will receive a series of Amazon gift cards as compensation for time throughout the study.

Join today

Interested in helping advance research on COVID-19 outcomes for immunocompromised individuals? Click below to see if you are eligible to participate!

CTA: Let's Go

Questions? Reach out to us at [contact]

[LINK TO MDH web and app stores]

Heading (claims): **Diagnosis Confirmation** Body: The claims data from your health plan indicate a previously diagnosed condition that we need to learn more about for the purposes of this study. Please upload a document confirming your diagnosis on the next screen. This can be a doctor's note, a screenshot of your EHR diagnosis list, lab work, test results or medication list. Accepted file types are [list of file types]. If your document is another type, please email it to the study team at [contact] **Button Text:** Next Heading (no claims): **Diagnosis Confirmation** Body: Thank you for your participation! Please upload a document confirming your diagnosis or age on the next screen. This can be a doctor's note, a screenshot of your EHR diagnosis list, lab work, test results or medication list. Accepted file types are [list of file types]. If your document is another type, please email it to the study team at [contact] **Button Text:** Next

Heading: [None]

Body: [None]

Button Text: Capture or Upload Image
Heading: Thank you
Body: Thank you for confirming your medical information. We will be reviewing the document you uploaded and will notify you when we are ready for you to continue with the study.
Button Text: Done
Heading: Document Review
Body: Our research coordinator is currently reviewing the document you uploaded confirming your diagnosis or age. This process can take a few business days, we appreciate your patience.
No further action is required on your part. We will notify you once we complete our review so you can continue with the study.
Button Text: Done
Heading: Baseline survey
Body: Help us learn about other diagnoses and understand any differences between demographic groups, such as income, race, ethnicity, and age.
Button Text: Next
[Baseline survey questions here; see Appendix 3]

Pre-conditions: Participant randomized into treatment arm
Heading: Thank you
Body: Thank you for sharing this information with the study team.
You have been randomized to the treatment group.
As such, the next step is to register an account with Cue Health and download their app on your smartphone. You will also order your testing kit through the mobile app.
Continue to the next task for additional instructions.
Button Text: Done
Pre-conditions: Participant randomized into control arm
Heading: Thank you
Body: Thank you for completing all of the onboarding activities.
You have been randomized to the control group.
This means you will come back to this app monthly to tell us how things are going and answer a few questions. Your \$20 Amazon gift card for completing onboarding will be available shortly. In the future, you will receive a \$10 Amazon gift card for each monthly survey you complete.
Button Text: Done

Pre-conditions:

Participant randomized into intervention arm

Heading:

Cue+ Membership

Body:

To begin, you must create an account with Cue Health using the link we will give you next. This link is unique to you and must not be shared with anyone else.

As a participant in our study, you have access to 10 Cue Health tests per month for free.

When creating your Cue account, you must use the email address you previously gave us to ensure you receive your testing kit at no cost. Make sure it appears below correctly. If you need to change it, exit this survey and go to the Account tab.

Email: [read-only, pre populated input field]

Button Text:

Next

Heading:

Create Cue Health account

Body:

Create an account with Cue Health using the link below.

You will be placing the order for \$0.

Cue Health [link to Cue+ order page on Cue Health website]

Remember to use the email address we have on file.

Button Text:

Next

Heading:

[None]

Body:
Now that you have created an account with Cue Health, you may download the app on your smartphone.
Search for Cue Health on your smartphone's app store. It should look like one of the two screenshots below depending on your device.
Once you've found it, proceed to installing it and sign in.
[Two cropped screenshots showing Cue Health logo and app name]
Button Text: Next
Heading: [None]
Body:
Have you successfully installed the Cue Health app and signed in?
[] Yes [] No
Button Text: Next
Heading:
Order a Cue test kit
Body:
Great! You may now order your testing kit.
In the Cue Health app, order the 10 COVID-19 Tests & Cue Reader. Since you are a study participant, you should see \$0 as the price for the package.
Button Text:
Next
Heading:

[None]

Body: Have you successfully placed an order for the testing kit?
[] Yes [] No
Button Text: Next
Heading: Thank you
Body: Thank you for completing this task.
Once you receive the testing kit, return to the app and let us know. You'll get familiarized with the kit at that point and take your first test.
Button Text: Done
Heading: Take test
Body: Open your testing kit package and get familiarized with its contents. Proceed to take a baseline COVID-19 test with this device.
Button Text: Next
Heading: [None]
Body: Have you taken your first test with the Cue Health kit?
[] Yes [] No

Button Text: Next
Heading: Thank you
Body: Thank you for completing this task.
Please remember to take a Cue COVID-19 test when you may have been exposed or are experiencing symptoms. If someone in your household may have been exposed to COVID-19 or is symptomatic, give them a test to use. Please set up profiles in the Cue App for each person who uses Cue tests.
We'll also notify you next month when it's time for your check-in.
Button Text: Done
Heading: Monthly check-in
Body: Thank you for your continued participation in this study.
This survey is intended to capture information about how you have been feeling and any COVID-19 exposures and infections you have had since we last checked in.
Once you complete this survey, you will earn a \$10 Amazon gift card to thank you for your time.
Button Text: Done
[Monthly check-in survey questions here; see Appendix 3]
Heading: Thank you

Please remember to take a Cue COVID-19 test when you may have been exposed or are experiencing symptoms. If someone in your household may have been exposed to COVID-19 or is symptomatic, give them one test to use. You can set up a profile for them ir your Cue App.
Button Text: Done
Heading: Amazon Gift Card
Body: You are now eligible for a [\$20 \$10] Amazon gift card.
[Gift card code]
In order to use your gift card, add it to your Amazon.com account.
Button Text: Done
Heading: [None]
Body: Have you taken your first test with the Cue Health kit?
[] Yes [] No
Button Text: Done
Heading:

Thank you for sharing this information with the study team. Your Amazon gift card is now

Body:

available.

When to test

Body:

You should use your Cue Health Molecular COVID-19 test if you may have been exposed to COVID-19 or notice any of the following symptoms, or think you might be getting sick:

- Fever
- Chills
- Congested or runny nose
- Cough
- Sore throat
- Congestion
- Stomachache
- Headaches
- Body aches
- Fatigue
- Neck pain
- Shortness of breath
- Chest tightness
- Sneezing
- Wheezing
- Weakness

If someone in your household may have been exposed to COVID-19 or is experiencing any of these symptoms, you can set up a Cue profile for them in your Cue account and provide them with a test.

Button Text:

Done

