We plan to conduct a randomized control trial with 10,000 participants. Participation will last for a minimum of 4months and maximum of 8 months, depending upon COVID-19 case rates. Half of participants will be randomized to the control group and continue their existing testing and healthcare practices. The remaining participants will be randomized into the intervention arm. Participants in the intervention will receive one Cue Cartridge Reader for the duration of the study and up to 10 Cue COVID Molecular tests per month for their own

use and to share with others who could expose them to COVID-19 (e.g. close contacts). In the case that a Cue Flu+COVID Molecular Test is available through FDA EUA or other authorization, participants may be provided this multiplex test in lieu of the Cue COVID Molecular Test.

[figure not shown]
Table 1. Summary of Study Arms

Study Arm	Number of participants	COVID-testing practice
Control	5,000	None within this study
Intervention Arm	5,000	10 Cue tests per month to participants' for self and close contact use. Option to utilize Cue's telehealth and Rx delivery.

All intervention participants will be asked to test themselves if they are exposed or when symptoms arise. The primary outcome will be the number of hospitalizations that will be assessed from survey and claims data. We will also compare infection rates, ICU admissions, ED visits, deaths and cost of care between the control and intervention group. Our hypothesis is that access to high sensitivity portable molecular testing and subsequent antiviral treatment will significantly decrease hospitalization and thereby the cost of care.

Interested individuals will access the study via the MyDataHelps platform by web or app to complete the eligibility and informed consent process. Within the MyDataHelps experience, participants will complete study activities such as surveys and optional sharing of claims data. Participants who are randomized to the intervention group will have the option to use Cue Care should they test positive for COVID-19. In the case that the COVID Flu+COVID test is available, the intervention group will also have the option to use Cue Care should they test positive for Influenza. Cue Care contracts licensed Healthcare providers to deliver telemedicine and treatment for COVID-19.

Figure 1: Participant Flow

Study Population

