To meet our study objectives, participants who enroll will be considered moderately to severely immunocompromised, this can be due to several types of conditions and treatments. Participants will provide documentation from a medical provider confirming their diagnosis. We will also enroll those who are 65 years or older, with no immunosuppressive diagnosis, due to the risk of severe outcomes and hospitalization within this age group. Additionally, because Medicare is widely used in this population, connecting Medicare claims for those enrolling by age will be required. This portion of participants will make up no more than 25% of the study population.

Inclusion Criteria

- Living in the United States
- 18 years or older
- Can read and understand English
- Use of compatible device (as described in Appendix B)
- Vaccinated against COVID-19 (completed at least the initial course, e.g. at least 2 doses of Moderna or Pfizer, one dose of J&J)
- Willing and able to participate in study interventions including:
 - Use of smartphone, including camera and bluetooth
 - Upload verification of diagnosis, if needed
 - Completing Surveys
 - Use of Cue Health App
 - Use of MyDataHelps Web or App
- Belonging to one of these two groups:
 - o Immunocompromised due to disease or therapy, including:
 - Symptomatic HIV
 - Graft versus host disease
 - Immunoglobulin deficiency/Immunodeficiency
 - Immunosuppressive therapy
 - Leukemia
 - Lymphoma (Hodgkin or non-Hodgkin)
 - Metastatic Cancer
 - Multiple Myeloma
 - Solid organ malignancy
 - Transplant, hematopoietic stem cell
 - Transplant, solid organ
 - 65 years of age or older

Confirmation of immunocompromised status or age will be performed in one of three ways. Participants will be able to 1) upload a document directly into the MyDataHelps app, 2) email it to a study coordinator, or 3) have their eligibility automatically verified via claims data, if connected. Methods 1 and 2 will require the study team to review and confirm diagnosis prior to prompting the participant to complete the next study activity. Participants

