will be notified by push notification, email and/or SMS (depending on their notification preferences) that their diagnosis has been verified and they are eligible to move forward to participation. Method 3 will be automated back end verification of diagnosis and/or immunosuppressive medication history in MyDataHelps using the participants connected claims data for identification of qualifying ICD-10 diagnosis codes.

[figure not shown]
Study Interventions

All Groups (n=10,000)

Baseline study activities for all groups include: verification of immunocompromised status, downloading MyDataHelps or using the web version, completion of digital informed consent, baseline survey completion, optional connection to claims data source, monthly survey completion and reimbursement for participation.

Control Group (n=5,000)

[figure not shown]
Participants in the control group will complete the baseline study activities, as described above. If symptoms arise or COVID-19 infection occurs, participants will test and seek care as they normally would.

Intervention Arm (n=5,000)

Participants in this group will complete the baseline study activities, as described above. Additionally, participants will be instructed to create a Cue Health account and download the Cue Health App. Using the app and the 10 Cue Health COVID-19 molecular tests that are provided (or Cue Health Flu+COVID molecular tests if available and FDA authorized), the participant will perform tests after exposure or

symptoms arise. Participants can also use the test for close contacts who are exposed to COVID-19 and/or have symptoms. If COVID-19 infection occurs, participants will have access to telemedicine to discuss further with a healthcare professional. When clinically indicated, medication for the treatment of COVID-19 (and/or Influenza in case of Cue Health Flu+COVID test availability) will be prescribed and delivered to the participants' delivery address. Participants can also seek care through other healthcare providers or not seek care, at their discretion.

Device Use and Procedures

CareEvolution MyDataHelps Web or App

MyDataHelps by CareEvolution is the app or website that participants will use for digital consent, surveys, optional connection of claims data and reimbursement. In-app content can be reviewed in the appendices.

The Cue Health Monitoring System

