phone numbers, secondary contacts, and birth dates from participants who cannot share their claims data. Participants and their secondary contacts will only be called at the end of the study, by a research coordinator, to ask participants to complete surveys and remind them about reimbursement opportunities. Participants will be considered lost to follow up after three phone calls. Birth dates will be used to search the national death index.

Outreach

Center for Equitable and Diverse Research (CEDR), a division of the Institute for Public Health at SDSU. CEDR will be involved in conducting in-person outreach and education, study recruitment, and technical assistance as needed to help participants in San Diego County complete study requirements including the 1) eligibility survey, 2) using and navigating the MyDataHelps Web or App including assistance in completing monthly questionnaires, 3) creating the CUE Health App account, 4) completion of the informed consent process, 5) confirmation of immunocompromised status or age and 5) navigation of the CUE Health app.

CEDR will utilize a multi-strategy approach to study recruitment that will use the Community Health Worker/Promotores (CHW/P) model to conduct individual and group outreach and education activities with community members, community clinics, senior centers, and community organizations. Example activities include outreach at health fairs, community clinic waiting rooms, patient groups and senior centers; provider education to generate patient referrals; and partnerships with community-based organizations and advocacy groups to raise awareness with the community members they serve. During all outreach and education activities, prospective study participants will be asked for consent to voluntarily provide their contact information for follow-up calls and text messages to support enrollment and study retention. CEDR will share the IRB-approved outreach one-pager found in Appendix 4 with interested participants which will include the CEDR email address and phone number for those who have questions about the study. Talking points for use by outreach staff while speaking with participants about the study can be found in Appendix 25.

Risks and Benefits of Participation

The risks of participating in this study are minimal.

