Appendix 21: ImmunoCARE Animated Explainer Video | Script

INTRO & INCENTIVE

- People who are immunocompromised or over the age of 65 are still at high risk of developing severe disease from COVID-19, but a new study could help reduce that risk.
- The ImmunoCARE study is enrolling 10,000 participants nationwide and is providing some participants with free highly sensitive at-home COVID tests, access to telemedicine and delivery of antiviral medications. All participants will get Amazon gift cards as a thank you for taking part.
- · Interested? Keep watching to learn more, or head to immunocare.scripps.edu to get started.
- Scientists at the Scripps Research Digital Trials Center are investigating if early detection and rapid treatment can reduce COVID-19 hospitalizations among immunocompromised people and those over 65.
- The study is fully remote, meaning you won't need to visit a clinic or have in-person consultations.

ELIGIBILITY & ACCOUNT SET UP

- To find out if you are eligible to participate, you'll need to visit the study website and complete a brief survey.
 - o TEXT ON SCREEN (NOT PART OF SCRIPT):
 - § Live in the United States
 - § 18 years or older

- § Access to smartphone
- § Vaccinated against COVID-19
- § Diagnosed as moderately to severely immunocompromised, or be 65 years or older
- § Willing to participate in all study activities
- If you are eligible to participate, you will be prompted to create an account on the study web app, complete the informed consent process and fill out a short baseline survey.

SYNCING HEALTH PLAN

- Next, you will also be asked to connect to your health plan. This allows scientists to verify your immunocompromised status or age and study any medical care you received through your plan related to COVID-19. We use strict privacy practices.
- If it cannot be verified through your health plan data, you will need to provide proof of your immunocompromised status or age by sharing a document directly with the study team.

INTERVENTION

- Once your status is verified, you will be randomly assigned to either the control arm or the intervention arm. It is important to have participants in both of these groups so scientists can accurately determine whether the intervention is working.
- Those assigned to the control arm will complete a monthly survey about any COVID-19 exposures and diagnosis. If they develop symptoms, they will test and seek care as they normally would.

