- Those assigned to the intervention arm will also complete a monthly survey and create an account on the Cue Health mobile app. These participants will receive 10 Cue Health COVID-19 molecular at-home tests each month. Participants will perform tests after exposure or if symptoms arise. The tests can also be used for members of the same household, who have been exposed to COVID-19 or have symptoms.
- These nucleic acid amplification tests detect the genomic RNA of SARS-CoV-2, the virus that causes COVID-19, and are much more sensitive than more common rapid antigen tests.

If a test is positive, participants can consult with a healthcare professional through the Cue Health app. When clinically indicated, medication for the treatment of COVID-19 will be prescribed and delivered to the participant's home. Participants can also seek care through their own healthcare provider, or not seek care at their discretion.

OUTRO

- The scientists expect the study to run for up to 8 months. Participation is voluntary and you can withdraw at any time.
- Help us support those who are still at high risk of severe outcomes from COVID-19.
- For more information, visit immunocare.scripps.edu

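### With no household limit on enrolment, individual randomization and an instruction to share Cue tests at home, controls can receive the study's tests, which dilutes any between-arm comparison

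*Combined protocol and SAP*

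**What the plan says.** **Who can enter.** The Inclusion Criteria describe single persons, each "Belonging to one of these two groups": immunocompromised, or 65 or older. Age-only entrants must connect Medicare claims and may form at most 25% of the study. The Eligibility Survey (Appendix 3) asks nothing about other household members.

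**How they are assigned.** Study Design splits participants equally between arms. The explainer script (Appendix 21) says: "Once your status is verified, you will be randomly assigned to either the control arm or the intervention arm". No household or cluster rule is given.

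**What the intervention arm is told.** Under Study Interventions: "Participants can also use the test for close contacts who are exposed to COVID-19 and/or have symptoms". Appendix 21 adds: "The tests can also be used for members of the same household". The in-app text shown after the first test turns this permission into an instruction, "If someone in your household may have been exposed to COVID-19 or is symptomatic, give them a test to use", and asks for a Cue profile for each user. None of these places makes an exception for a household member who is a control.

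**What controls should get.** Table 1 gives their testing as "None within this study". Study Interventions leaves them to their usual testing and care.

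**What the plan allows for.** Table 2 allows 5% for drop-out and 20% for non-reporting, with nothing for contamination. The Baseline, Monthly and End of Study surveys do not ask whether a household member is enrolled or which test was used.

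**The concern.** Take two people who share a home and both qualify. Randomized separately 1:1, they fall in different arms half the time. The app then tells the intervention member to give the control member a molecular test when that person is exposed or ill. This is the intervention delivered as designed, so deviation monitoring has no reason to flag it.

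Such a control gains part of what the trial evaluates, namely early detection by a sensitive test, and can take a positive result to their own doctor. If early testing reduces hospitalization, the control rate drops and the observed difference shrinks. The stated power at the 900-case target is only 0.76, so there is little room for dilution. Co-enrolment is plausible: the Outreach section sends staff to "patient groups and senior centers", among other places, and an immunocompromised person and a spouse over 65 can both qualify.

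**Working it through.** **Inputs from Sample Size and Data Analysis.** Control hospitalization per case: 0.75 × 28% + 0.25 × 10% = 23.5%. Intervention: 23.5% × 0.70 = 16.45%. Target: about 450 cases per arm. Alpha 0.05; sidedness is not stated.

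**Step 1: reproduce the plan's power.** For two proportions with n per arm, power = Φ[(d − 1.96 × se0) / se1]. Here d is the difference in rates, se0 uses the pooled rate and se1 the separate rates.
- d = 0.235 − 0.1645 = 0.0705; se0 = 0.02665; se1 = 0.02655.
- z = (0.0705 − 1.96 × 0.02665) / 0.02655 = 0.688, so power = 0.754.

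This matches the stated 0.76 to rounding. A one-sided test would give 0.842 and does not match.

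**Step 2: from shared households to affected controls (assumed).** Let s be the share of participants who live with one co-enrolled person. Under independent 1:1 allocation, the share of controls with an intervention housemate is c = s/2. So s = 10% gives c = 5% (250 of 5,000 controls), and s = 20% gives c = 10% (500).

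**Step 3: dilute the control rate.** Control rate = 0.235 − c × r × e, where r is the hospitalization rate per case of the affected controls and e is the relative reduction they gain. Affected controls are taken to be infected as often as other controls. Three cases:
- full effect at the blended rate: r = 0.235, e = 0.30;
- half effect at the blended rate: r = 0.235, e = 0.15;
- full effect in age-only pairs, at the plan's rate for non-immunocompromised people over 65: r = 0.10, e = 0.30.

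| c | Case | Control rate | Observed ratio | Power, 450 per arm |
|---|---|---|---|---|
| 0 | none | 0.2350 | 0.700 | 0.754 |
| 5% | full, blended | 0.2315 | 0.711 | 0.713 |
| 5% | half, blended | 0.2332 | 0.705 | 0.734 |
| 5% | full, age-only | 0.2335 | 0.705 | 0.737 |
| 10% | full, blended | 0.2280 | 0.722 | 0.669 |
| 10% | half, blended | 0.2315 | 0.711 | 0.713 |
| 10% | full, age-only | 0.2320 | 0.709 | 0.720 |

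Example, c = 10%, full, blended: 0.235 − 0.10 × 0.235 × 0.30 = 0.22795, and 0.1645 / 0.22795 = 0.722.

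**Step 4: the age cap.** If every age-only entrant were paired with another, s would be 25% and c 12.5%. The control rate is then 0.235 − 0.125 × 0.10 × 0.30 = 0.23125, the ratio 0.711 and power 0.711. That is the ceiling for age-only couples.

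**Step 5: the 800-case minimum.** At 400 cases per arm, power is 0.704. With full effect at the blended rate it falls to 0.662 (c = 5%) or 0.618 (c = 10%).

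**The case against.** **The trial is closing.** Estimated Duration of Study says it ends early after the regulator's warning about the test, and that the data will mainly describe the pandemic's effect on this population. The 900-case power calculation no longer drives the analysis, and enrolment rules cannot help people already randomized. This stands. It leaves the point relevant to any between-arm comparison still reported, and to a restart or successor.

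**The rate is unknown.** Nothing in the documents says that spouses commonly join together. The senior-center outreach is described for San Diego County only, and recruitment also runs online and through a physician network. This stands, so only a range can be given.

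**Stronger readings that the documents do not support.**
- A reader might infer that these controls receive the whole intervention. The Cue Care section gives telehealth access to participants randomized to the treatment arm. It does not say that a household profile carries that access. Only the test is documented as shared.
- A reader might infer that Table 1 is false for them. Table 1 describes what the study supplies. Controls were never barred from testing.
- A reader might infer a serious loss of independence. Under individual randomization, pairs split across arms roughly offset pairs in the same arm, so variance inflation is negligible.
- A reader might infer that affected controls cannot be found. Cue profiles, date of birth, zip code and phone numbers may allow partial linkage, although none is planned. The Surveys section ties phone and second-contact collection to people who cannot share claims, so coverage may be uneven.

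**Silence.** The consent pages and the pages just before the in-app onboarding text were not available, so a household rule there cannot be excluded.

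**Conclusion.** The mechanism holds on the visible text: person-level eligibility, individual randomization and an instruction to share tests at home, with no exception for controls. If testing helps, the bias is toward no difference.

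The size is uncertain and probably modest. Power falls from 0.754 to about 0.71-0.74 if 5% of controls are affected, and to about 0.67-0.72 if 10% are. The observed ratio moves from 0.70 to at most 0.711 and 0.722. The lower power figures are an upper bound on harm for controls of average risk, because they credit a shared test alone with the full 30% reduction. If few households are shared, the effect is close to nil. The values of c, s and the effect carried by a shared test are assumptions; the other inputs are the plan's own.

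This is worth correcting in a reused design, and worth a sensitivity analysis and a stated limitation in this one. It does not by itself invalidate a comparison of the arms.

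**What to change.** **If enrolment resumes or the design is reused**, choose one:
- Add a screener item and matching criterion: no other member of the household is enrolled in ImmunoCARE. Cost: one question and a few lost recruits.
- Assign later household members to the first member's arm and cluster the variance by household. Cost: later members join knowing their arm, and there is a small design effect of 1 + s × ICC. With an assumed ICC of 0.2, s = 10% gives 1.02 and power 0.746; s = 20% gives 1.04 and 0.738.

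**For participants already enrolled:**
- If the End of Study Survey is still open, add one item in both arms: whether anyone else in the household took part, and whether the respondent used a Cue test during the study. Otherwise link by Cue app profiles and baseline contact data, and report how complete the linkage is.
- Report any between-arm comparison as randomized. Add a sensitivity analysis that excludes every multi-enrollee household from both arms. Keeping only the first enrollee would retain a control whose partner later joined the intervention arm. Cost: some lost events. Because the second member's decision to join may depend on the first member's arm, this should not replace the randomized comparison.
- State possible sharing of tests with controls as a limitation, with its direction.
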